- g BFI is a 5 minute self-assessment tool that identifies fatigue in cancer participants over a 24-hour period.
- h The first TUG assessment is to be performed before the first dose (either during screening or Week 1 Day 1).
- i Once the baseline procedures are completed, the first administration of study intervention will be provided at the study center and the participant will be provided with additional medication to take as scheduled through the Week 4 visit. (Each participant will be instructed to bring any remaining drug back to the center at the Week 4 visit.)
- j At this and each subsequent visit, the participant will return dispensed but unused study intervention to the investigator for recording on the CRF. Reasons for non-compliance will be recorded. A new supply of study drug sufficient to meet the dosing requirements of each participant will be dispensed.
- k Participants remaining on treatment beyond Week 52 will continue, where possible, to receive study intervention and assessments until the final evaluation of the randomized phase (i.e. at Week 52 for the last participant, see Section 4.4.1).
- l Prior to the final evaluation of the randomized phase of the study, all participants will go into Week 53 active follow-up or survival follow-up as applicable.
- m Each participant should complete an end of treatment visit after discontinuation of study intervention for any reason. All anti-cancer treatments after discontinuation of study intervention in this study will be recorded on the CRF at the end of treatment visit. See Section 4.4.2 for more details once the date of the final evaluation of the randomized phase is determined.
- n Survival will be followed with contact with the participant and/or his caregiver every 3 months following the date of last treatment until the end of the study for participants treated with darolutamide (see Section 4.4.2).

Table 1–2 Schedule of Activities for the Randomized Phase (darolutamide, enzalutamide)													
Assessment	Screening	Randomization	Intervention + Observation Period									End of treatment visit (30 days after last dose) ⁿ	Survival follow-up ^{m,o}
			Week 1 Day 1 ⁱ	Week 4 ^k	Week 8	Week 12	Week 24	Week 38	Week 52	from Week 53: Active follow up every 3 months ^{l,m}			
Time window allowed	within 21 days prior to randomization		within 21 days after randomization	± 7 days	± 7 days	± 7 days	± 7 days	± 14 days	± 7 days	± 1 month	+ 1 month	± 1 month	

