4.1 Overall Design

This is a randomized, open-label, multicenter, Phase 2b study to be conducted with a total of approximately 150 participants with CRPC who have not previously been treated with apalutamide, darolutamide, or enzalutamide. CRPC patients with a history of treatment with abiraterone may be eligible if they have not progressed and discontinued treatment within 6 months before signing the ICF for this study.

The study consists of two phases, a lead-in phase and a randomized phase (see Figure 1–1). In the lead-in phase, approximately 30 participants will be treated with darolutamide. Following the primary evaluation of the lead-in phase, approximately 120 participants will be randomized in a 1:1 ratio to receive either darolutamide (600 mg twice daily) or enzalutamide (160 mg once daily) in the randomized phase of the study. Randomization will be stratified by age (<75, ≥75 years).

At the end of the lead-in phase of the study, the compliance and variability of the endpoints and overall feasibility of the study execution will be assessed. The randomized phase of the study will start only after the primary evaluation of the lead-in phase. Depending on the results of the evaluation, the primary endpoint for the randomized portion of the study may be changed. The final study design and endpoints for the randomized phase will be determined based on the lead-in cohort of 30 participants. The decision to move to the randomized phase of the study will involve reviewing the findings from the lead-in phase of the study with the members of the steering committee.

The primary evaluation of the lead-in phase will occur when at least 30 participants in the lead-in phase have been on the study for at least 24 weeks, unless the participant discontinued due to lost to follow-up, withdrawal, or death. Additional participants may be enrolled in the lead-in phase if necessary.

The following endpoints will be evaluated at the end of the lead-in phase:

- the proportion of participants with a worsening in TUG time at week 12 and 24 and during the 24-week and 52-week period from baseline. Worsening is defined as an increase of at least 1 second in TUG time from baseline.
- the proportion of participants with a worsening in SPPB total score at week 12 and 24 and during the 24-week and 52-week period from baseline. Worsening is defined as a decline of at least 0.5 points in SPPB total score.

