4.4 End of Study Definition

4.4.1 Final evaluation of the randomized phase

The final evaluation of the randomized phase will be at least 52 weeks from the initial dose of the study drug of the last participant randomized in the study, unless the participant discontinued due to lost to follow-up, withdrawal, or death.

If the trial is stopped but benefits are observed for ongoing participants, options for treatment continuation will be discussed and agreed between the investigator, sponsor and the participants.

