9.4 Statistical Analyses

The statistical analysis plan (SAP) will be developed and finalized before database lock and will describe the participant populations to be included in the analyses and procedures for accounting for missing, unused, and spurious data. This section is a summary of the planned statistical analyses of the primary and secondary endpoints. Additional exploratory analyses of the data will be conducted as deemed appropriate.

All variables will be analyzed with appropriate statistical methods: categorical variables by frequency tables (absolute and relative frequencies) and continuous variables by sample statistics (i.e., mean, standard deviation, minimum, median, quartiles, and maximum). Continuous variables will be described by absolute value and as change from baseline per analysis time point, if applicable.

The primary analysis for the lead-in phase of the study will occur when the last participant has been on the study for at least 24 weeks, unless the participant discontinued due to lost to follow-up, withdrawal, or death. The primary analysis for the randomized phase of the study will occur when the last participant has been on the study for at least 24 weeks, unless the participant discontinued due to lost to follow-up, withdrawal, or death. The final analysis for the randomized phase of the study will occur when the last participant has been on the study for at least 52 weeks after the start of study intervention, unless the participant discontinued due to lost to follow-up, withdrawal, or death. Separate analyses will be performed for the lead-in phase and the randomized phase of the study. Participants will not be pooled across the two phases of the study.

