9.5 Interim Analyses

No formal interim analyses are planned in this study. However, this study will be conducted in two phases and the primary analysis for the lead-in phase will be performed when the last participant in the lead-in phase has been on the study for at least 24 weeks, unless the participant discontinued due to lost to follow-up, withdrawal, or death. The decision to move to the randomized phase of the study will involve reviewing the findings from the lead-in phase of the study with the members of the steering committee.

The primary analysis for the randomized phase for the study will occur when last participant in the randomized phase of the study has been on the study for at least 24 weeks, unless the participant discontinued due to lost to follow-up, withdrawal, or death. A final analysis for the randomized phase for the study will occur when last participant in the randomized phase of the study has been on the study for at least 52 weeks, unless the participant discontinued due to lost to follow-up, withdrawal, or death.

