### 3.0 Study Design

#### 3.1 Overall Study Design

This randomized, open-label, multicenter, Phase 2b study is designed to evaluate physical function, including balance and daily activity, in

[figure not shown]
participants with CRPC, treated with darolutamide (or enzalutamide in randomized phase). It will also evaluate, safety, cognitive function, fatigue, and survival.

The study consists of two phases, a lead-in phase and a randomized phase. In the lead-in phase, approximately 30 participants will be treated with darolutamide. The lead-in phase analysis will be performed when the last participant in the lead-in phase has been on the study for at least 24 weeks, unless the participant discontinued due to lost to follow-up, withdrawal, or death. The decision to move to the randomized phase of the study will be conditional on the findings of the lead-in phase which will be reviewed with the members of the steering committee. Findings of the lead-in phase will determine feasibility to move on or not with a randomized phase. If determined feasible and decided to proceed with the randomized phase, the appropriate endpoint and the time point and time frame of evaluation of the endpoint for a randomized part of the study will be chosen and the sample size will be reassessed.

In the randomized phase, approximately 120 additional participants will be randomized in a 1:1 ratio to receive either darolutamide (600 mg twice daily) or enzalutamide (160 mg once daily) in the randomized phase of the study. Randomization will be stratified by age (<75, ≥75 years).

The endpoints used in this study are novel in a way that, decline in physical function, will be evaluated using objective measures such as TUG, SPPB, and accelerometry, therefore, the lead-in phase has been added to be able to assess compliance and the variability of the endpoints and overall feasibility of the study execution. The randomized phase of the study will start only after a decision is made based on the findings from the primary analysis of the lead-in phase as described above.

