## **5.4 Efficacy Analyses**

The primary analysis for the lead-in phase of the study will occur when the last participant has been on the study for at least 24 weeks, unless the

participant discontinued due to being lost to follow-up, withdrawal, or death.

The final analysis for the randomized phase of the study will occur when the last participant has been on the study for at least 52 weeks after the start of study intervention, unless the participant discontinued due to being lost to follow-up, withdrawal, or death.

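### The only dated lead-in analysis is at 24 weeks, so the planned 52-week lead-in endpoints and later lead-in safety, exposure and PSA data have no scheduled analysis

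*Protocol*

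**What the plan says.** **Analysis dates.** "In the lead-in phase, approximately 30 participants will be treated with darolutamide" (Protocol 4.1). Protocol 9.5 states that "the primary analysis for the lead-in phase will be performed when the last participant in the lead-in phase has been on the study for" a minimum of 24 weeks. SAP 5.4 agrees, counting in weeks: "The primary analysis for the lead-in phase of the study will occur when the last participant has been on the study for at least 24". SAP 3.1 refers to this simply as the analysis of the lead-in phase. The only other end-stage analysis is tied to the other phase: "A final analysis for the randomized phase for the study will occur when last participant in the randomized phase of the study has been on" (Protocol 9.5; the period given there is a minimum of 52 weeks). Protocol 9.4 adds: "Participants will not be pooled across the two phases of the study".

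**The randomized phase is conditional.** SAP 3.1: "Findings of the lead-in phase will determine feasibility to move on or not with a randomized phase".

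**Lead-in follow-up goes well beyond 24 weeks.** Protocol Table 1–1 schedules lead-in visits at Weeks 38 and 52 and then every 3 months. Footnote k reads: "Participants remaining on treatment beyond Week 52 will continue, where possible, to receive study intervention and assessments until the final evaluation of the randomized phase". Protocol 4.4.1 counts that evaluation from the last man randomized: "The final evaluation of the randomized phase will be at least 52 weeks from the initial dose of the study drug of the last participant".

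**52-week lead-in results are planned.** Protocol 4.1 lists TUG and SPPB worsening over both 24 and 52 weeks for evaluation at the end of the lead-in phase. SAP 5.1 applies its analyses to both phases unless it says otherwise. SAP 5.5.2 includes TUG and SPPB worsening at any time up to 52 weeks, and SAP 5.4.2 includes PSA response at 52 weeks.

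**The concern.** The plan asks for 52-week lead-in results but dates only one lead-in analysis, set by the last participant reaching 24 weeks. At that cut the 52-week proportions would rest on incomplete follow-up. The go/no-go decision waits for this analysis, so there is pressure to run it as soon as the trigger is met.

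After the cut, lead-in men go on generating adverse events, falls, fractures, dose changes and PSA values. The randomized-phase final analysis cannot pick these up by pooling, and it will not take place if that phase does not open. In that case the lead-in men are the trial's entire dataset, and their later outcomes have no prespecified reporting point.

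**Working it through.** **The plan's own figures.** The documents give no figure for this point. The lead-in precision table (Protocol Table 9–1, exact binomial, n = 30) reproduces in all six rows; for example, 6 of 30 gives 7.71% to 38.57%. It takes all 30 men as the denominator. The question is how many of them could have 52 weeks of data at the planned cut.

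**Inputs.** 30 men (Protocol 4.1). Cut at 24 weeks after the last man enters (Protocol 9.5, SAP 5.4). Horizon of 52 weeks (Protocol 4.1, SAP 5.5.2). Accrual time *A* is not stated, so a range is shown. Assumptions: even accrual, no dropout, and the cut made at exactly 24 weeks.

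**Formulas.** Man *i* (*i* = 0 to 29) enters at *t_i* = *A* × *i*/29 and has *f_i* = 24 + *A* − *t_i* weeks at the cut. He could have reached Week 52 if *f_i* ≥ 52, that is, if *t_i* ≤ *A* − 28. The observed share of first-year person-time is the sum of min(*f_i*, 52) divided by 30 × 52. When *A* ≤ 28 no man exceeds 52 weeks, and the share reduces to (24 + *A*/2)/52.

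- *A* = 0: 24/52 = 46%
- *A* = 13: 30.5/52 = 59%
- *A* = 26: 37/52 = 71%
- *A* = 39: *t_i* ≤ 11 gives *i* ≤ 8.2, so 9 men
- *A* = 52: *t_i* ≤ 24 gives *i* ≤ 13.4, so 14 men
- *A* = 78: *t_i* ≤ 50 gives *i* ≤ 18.6, so 19 men

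| Accrual (weeks) | Men who could have reached Week 52 | First-year person-time observed | Not observed |
|---|---|---|---|
| 0 | 0 of 30 | 46% | 54% |
| 13 | 0 of 30 | 59% | 41% |
| 26 | 0 of 30 | 71% | 29% |
| 39 | 9 of 30 | 80% | 20% |
| 52 | 14 of 30 | 85% | 15% |
| 78 | 19 of 30 | 90% | 10% |

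**What this does to the 52-week endpoint.** In Table 1–1, TUG and SPPB are measured at Weeks 12, 24 and 52, and not at Week 38. With accrual of 26 weeks or less the first man is at most 50 weeks in (24 + 26), before the Week 52 visit window opens at Week 51. On scheduled visits, the proportion worsening by 52 weeks would then simply repeat the proportion worsening by 24 weeks. With slower accrual it would mix men who have a Week 52 visit with men who do not.

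**The lead-in outputs.** SAP 9.0 lists lead-in adverse event, serious adverse event, PSA and death outputs with no cut-off date and no second run. It lists no exposure table and no table for adverse events of interest. SAP 5.5.2 limits lead-in accelerometry to Weeks 12 and 24 but gives the randomized phase Week 52 as well. SAP 5.4.2 excludes overall survival from the lead-in.

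**The case against.** A reader might infer that every later milestone for the lead-in men hangs on the randomized phase. The documents do not support that. Protocol 4.1 runs the study to 52 weeks after the last participant's initial dose without requiring that he was randomized. Section 4.4.2 defines completion by the 52-week evaluation. Section 4.4.3 ends the study with the last darolutamide-treated participant. Section 7.1 keeps men who stop treatment under evaluation for 52 weeks. These points stand. They are conduct milestones, however, and none of them triggers an analysis. Section 6.7 also ties study duration to the last participant randomized, which differs from 4.1.

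A reader might also infer that later lead-in data will never be reported. That does not follow either. SAP 5.1 carries the analyses to both phases, SAP 5.5.5 counts treatment-emergent events to 30 days after the last dose, and SAP 5.5.4 sums dose over the whole study. The 24-week analysis is called primary and its trigger is a minimum, so a later cut or update is permitted. But nothing requires one, and SAP 5.1 sets scope and methods, not a data cut.

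Two limits on the importance of the point also stand. The lead-in is a feasibility phase without hypothesis tests (Protocol 4.1, 9.1). Serious adverse events reach the sponsor within 24 hours whatever the analysis date (Protocol 8.3.1), so individual safety reporting is not at risk.

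**Conclusion.** The concern holds as a gap in analysis timing. The one dated lead-in analysis does not fit the 52-week lead-in TUG and SPPB endpoints in Protocol 4.1 and SAP 5.1/5.5.2, and later lead-in adverse events, exposure and PSA outcomes have no scheduled analysis.

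Under even accrual and no dropout, between 0 and 19 of 30 men could have reached Week 52 at the cut across accrual times of 0 to 78 weeks. The unobserved share of first-year person-time falls from 54% to 10% over that range. The 52-week results are incomplete in every scenario examined, but the size depends on an accrual time that the documents do not give. Time after Week 52 is additional.

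The primary randomized comparison, its sample size and its power are unaffected. The gap matters most if the randomized phase does not open.

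**What to change.** 1. Add to Protocol 9.4 and 9.5 and SAP 3.1 and 5.4 a final lead-in analysis, performed when the last lead-in participant has completed Week 52 or left the study, whether or not the randomized phase opens. If that phase does not open, state that this is the final study analysis, with an update of safety, exposure and PSA at end of study.
2. Move the 52-week lead-in TUG and SPPB endpoints in Protocol 4.1 to that analysis and keep the 12- and 24-week results at the 24-week cut.
3. Add to the lead-in outputs in SAP 9.0 an exposure table and a table for adverse events of interest. Add the Week 52 lead-in accelerometry summary in SAP 5.5.2.
4. Reconcile Table 1–1 footnotes k and l with Protocol 4.1, 4.4.1, 4.4.2 and 6.7, so that it is clear which milestone applies to lead-in men if the randomized phase does not open. Which rule should govern continued treatment is for the sponsor to settle.

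The cost is one additional run of the lead-in outputs and a few added tables. No new patients, visits or data collection are needed, because the Week 52 assessments are already scheduled.

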9.5.1 Data Monitoring Committee (DMC)

Not applicable.

10. Supporting Documentation and Operational Considerations

10.1 Appendix 1: Regulatory, Ethical, and Study Oversight Considerations

10.1.1 Regulatory and Ethical Considerations

- This study will be conducted in accordance with the protocol and with the following:
 - Consensus ethical principles derived from international guidelines including the Declaration of Helsinki and Council for International Organizations of Medical Sciences (CIOMS) International Ethical Guidelines
 - Applicable ICH Good Clinical Practice (GCP) Guidelines
 - Applicable laws and regulations
- The protocol, protocol amendments, ICF, Investigator Brochure, and other relevant documents (e.g., advertisements) must be submitted to an IRB/IEC by the investigator and reviewed and approved by the IRB/IEC before the study is initiated.
- Any amendments to the protocol will require IRB/IEC approval before implementation of changes made to the study design, except for changes necessary to eliminate an immediate hazard to study participants.
- The investigator will be responsible for the following:
 - Providing written summaries of the status of the study to the IRB/IEC annually or more frequently in accordance with the requirements, policies, and procedures established by the IRB/IEC
 - Notifying the IRB/IEC of SAEs or other significant safety findings as required by IRB/IEC procedures
 - Providing oversight of the conduct of the study at the site and adherence to requirements of 21 CFR, ICH guidelines, the IRB/IEC, European regulation 536/2014 for clinical studies (if applicable), and all other applicable local regulations

10.1.2 Financial Disclosure

Investigators and sub-investigators will provide the sponsor with sufficient, accurate financial information as requested to allow the sponsor to submit complete and accurate financial certification or disclosure statements to the appropriate regulatory authorities. Investigators are responsible for providing information on financial interests during the course of the study and for 1 year after completion of the study.

All relevant documentation will be filed in the trial master file.

10.1.3 Informed Consent Process

- The investigator or his/her representative will explain the nature of the study to the participant or his/her legally authorized representative and answer all questions regarding the study.
- Participants must be informed that their participation is voluntary. Participants or their legally authorized representative will be required to sign a statement of informed consent that meets the requirements of 21 CFR 50, local regulations, ICH guidelines, Health Insurance Portability and Accountability Act (HIPAA) requirements, where applicable, and the IRB/IEC or study center.
- The medical record must include a statement that written informed consent was obtained before the participant was enrolled in the study and the date the written consent was obtained. The authorized person obtaining the informed consent must also sign the ICF.
- Participants must be re-consented to the most current version of the ICF(s) during their participation in the study.
- A copy of the ICF(s) must be provided to the participant or the participant's legally authorized representative.
- A participant who is rescreened is required to sign another ICF.

10.1.4 Data Protection

- Participants will be assigned a unique identifier by the sponsor. Any participant records or datasets that are transferred to the sponsor will contain the identifier only; participant names or any information that would make the participant identifiable will not be transferred.
- The participant must be informed that his personal study-related data will be used by the sponsor in accordance with local data protection law. The level of disclosure must also be explained to the participant.
- The participant must be informed that his medical records may be examined by Clinical Quality Assurance auditors or other authorized personnel appointed by the sponsor, by appropriate IRB/IEC members, and by inspectors from regulatory authorities.

10.1.5 Committees Structure

A steering committee will provide strategic direction, guidance and oversight for the study. This committee will meet approximately once a year or as required to keep track of issues and the progress of the study's implementation and activity.

No data monitoring committee, dose escalation committee, or similar review group will be used for this study.

